data strongly suggest that Aquamin® has the potential to improve barrier function in the gastrointestinal tract and that this may be part of its mechanism of action in individuals with UC; given the barrier permeability differences in IBS-D patients, Aquamin® also will likely improve barrier function and subsequently help ameliorate symptom burden in patients with IBS-D. In spite of this, there has not yet been an attempt to directly assess gastrointestinal barrier function *in vivo* in response to Aquamin® intervention (neither in healthy individuals nor in subjects with any inflammatory bowel disease). This is also not a part of the ongoing trial with UC sufferers. The goal of the proposed study is to address this issue. Our proposal is to enroll 12 subjects who are healthy adults, 12 subjects with UC in remission, and 12 subjects with IBS-D and provide 90-days of intervention with Aquamin® under conditions identical to those currently being used as part of the UC trial. Before and after intervention, we will use the lactulose:mannitol ratio in urine (22) as a way to assess effects of intervention on a direct measure of gut permeability.

Study aim: To determine whether Aquamin® taken daily, standardized to 800 mg of calcium per day for 90 days, will improve barrier function in the gastrointestinal tract as assessed using the lactulose:mannitol ratio in urine in healthy subjects, ulcerative colitis subjects, and diarrhea predominant irritable bowel subjects.

The primary outcome is an assessment of the barrier function, evaluated by a change in the lactulose:mannitol ratio in urine by comparing values at 90-days (post-intervention) to baseline (pre-intervention) levels. Pre- post-values will be measured and compared using appropriate statistical methods performed by the study biostatistician and the program GraphPad Prism, version 8.0 will also be used.

Approach:

Healthy Subjects: We will recruit and enroll 12 healthy subjects (i.e., not having UC) for this study. The inclusion and exclusion criteria for the healthy subjects is listed below.

Subjects with UC: We will recruit and enroll 12 subjects with UC. The inclusion and exclusion criteria listed in Section 4.5 and 4.6 (of the parent study and is listed below) will be used except use of anticoagulants will not be an exclusion.

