Subjects with IBS-D: We will recruit and enroll 12 subjects with diarrhea predominant irritable bowel syndrome. The inclusion and exclusion criteria for the IBS-D subjects is listed below.

Aquamin®: The study agent will consist of Aquamin® capsules. The capsules will be identical to those being used in the parent study. Subjects will receive an amount of Aquamin® sufficient to provide 800 mg of calcium per day. See Section 5 of the parent study for details of the study agent. Please note that in the proposed study, there will be no placebo group.

Inclusion Criteria for the healthy subjects:

- Must be able to give written informed consent.
- Be generally healthy, male or female, ages 18 to 80 years old.
- A negative pregnancy test for pre-menopausal women with intact female reproductive organs. The negative pregnancy test must be within 2 weeks of the baseline visit and the subject must agree to use appropriate birth control over the study period. Acceptable forms of

birth control include: hormonal (such as pill, IUD), barrier (such as condom, diaphragm), surgical, or abstinence. Post-menopausal is defined as no menses for the previous 12 months. If cessation of menses is within 12 months, then the subject should be treated as pre-menopausal and a pregnancy test performed.

Exclusion Criteria for the healthy subjects: The exclusion criteria are similar to the one listed in Section 4.6 for UC subjects (of the parent study) with few exceptions.

- Must not be pregnant or lactating; patients of childbearing potential unwilling to use acceptable birth control throughout the study also excluded.
- Must not be participating in any other interventional trial using an investigational drug.
- Subjects likely to be uncooperative or unable to comply with study procedures
- Participants must not have a history or diagnosis of any of the following conditions:
 - i. Crohn's disease, other inflammatory bowel disease, or a functional gastrointestinal disorder, including irritable bowel syndrome.
 - ii. Any stomach or intestinal bleeding disorders (gastrointestinal bleeding from gastric or duodenal ulcers, or gastrin secreting tumors) or active gastric / duodenal ulcers - peptic ulcer disease (without bleeding in last 3 months).
 - iii. Any gastrointestinal or colonic malignancy.
 - iv. Kidney disease, including kidney "stones" or hypercalcemia.
 - v. Coagulopathy/hereditary hemorrhagic disorders.
 - vi. Neurologic disease.

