 - Ulcerative colitis with confirmed diagnosis by histology and endoscopy; AND be in stable remission for 3 months or more without therapy or with a maintenance therapy (except steroids and antibiotics for 3 months) OR have mild ulcerative colitis. Note: Corticosteroids (a type of steroid drug such as prednisone or cortisol that helps the body to regulate stress response, immune response and inflammation) and antibiotics can be used during a flare-up once the study has begun and the subject enrolled.
 - A negative pregnancy test for pre-menopausal women with intact female reproductive organs. The negative pregnancy test must be within 2 weeks of the baseline flexible sigmoidoscopy, and subject must agree to use appropriate birth control over the study period. Acceptable forms of birth control include: hormonal (such as pill, IUD), barrier (such as condom, diaphragm), surgical, or abstinence. Post-menopausal is defined as no menses for the previous 12 months. If cessation of menses is within 12 months, then the subject should be treated as pre-menopausal and a pregnancy test performed.

Exclusion Criteria for subjects with ulcerative colitis:

- Female subjects must not be pregnant or lactating; and female of childbearing potential unwilling to use acceptable birth control throughout the study.
- Must not be participating in any other interventional trial using an investigational drug.
- Subjects likely to be uncooperative or unable to comply with study procedures
- Participants must not be felt to have active ulcerative colitis for 3 months before study enrollment (with the exception of mild ulcerative colitis).
- Participants must not have a history or diagnosis of any of the following conditions:
 - Crohn's disease.
 - Any stomach or intestinal bleeding disorders (gastrointestinal bleeding from gastric or duodenal ulcers, or gastrin secreting tumors) or active gastric / duodenal ulcers - peptic ulcer disease (without bleeding in last 3 months).
 - Any gastrointestinal or colonic malignancy.
 - Kidney disease, including kidney "stones" or hypercalcemia.
- Participants will be excluded if they have taken the following, within the last 30 days or are unwilling to forgo the following for 30 days prior to entry into the study:
 - Calcium, Vitamin D, including multivitamins that have low amounts of calcium/Vitamin D and fiber supplements.

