 - Non-steroidal anti-inflammatory medications (NSAIDs), such as Naproxen or Ibuprofen (except for occasional pain control or low dose aspirin for cardiovascular disease prevention). Note – IBD patients are cautioned to avoid NSAIDs in general since they are associated with flare of disease.

Inclusion Criteria for Irritable Bowel Syndrome Type D Patients:

- Must be able to give written informed consent.
- Patients with ages 18-80 years old.
- Must have the following to meet IBS-D Diagnostic Rome IV Criteria:
 - i. Recurrent abdominal pain on average at least 1 day/week in the last 3 months, associated with two or more of the following criteria:
 - a. Related to defecation
 - b. Associated with a change in frequency of stool (increased)
 - c. Associated with a change in form (appearance of stool)
 - ii. Symptom onset at least 6 months prior to diagnosis

- iii. Greater than twenty-five percent of bowel movements (BM) with Bristol Stool types 6 or 7 and less than twenty-five percent of bowel movements with Bristol stool types 1 or 2. BMs are usually diarrhea, “watery,” “liquid,” “fluffy pieces,” or “mushy”.
- A negative pregnancy test for pre-menopausal women with intact female reproductive organs. The negative pregnancy test must be within 2 weeks of the baseline visit and the subject must agree to use appropriate birth control over the study period. Acceptable forms of birth control include: hormonal (such as pill, IUD), barrier (such as condom, diaphragm), surgical, or abstinence. Post-menopausal is defined as no menses for the previous 12 months. If cessation of menses is within 12 months, then the subject should be treated as pre-menopausal and a pregnancy test performed.
- If currently on a mood medication, the subject must continue to have IBS symptoms like abdominal pain, bloating, bothersome constipation or diarrhea to be included. See below in exclusionary criteria for mood medications that would exclude participation in the study
 - the patients are allowed to be on the following medications throughout the study as long as the dosage and regimen is stable:
 - specific atypical antidepressants including trazodone, St John's wort
 - selective serotonin reuptake inhibitors including escitalopram, citalopram, fluoxetine, fluvoxamine, sertraline, paroxetine, and vortioxetine
 - second generation antipsychotics, including olanzapine, risperidone, and quetiapine

Exclusion Criteria for Irritable Bowel Syndrome Type D Patients:

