^C The pregnancy test which must be valid within 14 days of the first dose of study medication. If the time between visit 1 and visit 2 is greater than 14 days, the pregnancy test may be done at visit 2 only or be repeated.

^D IBDQ or IBS-QOL will be offered electronically and should be completed on Days 0, and 90 (+/- 5 days).

^E Given at visit 2 and collected at the visit 3 with reminders at phone monitoring.

^F For clinical and research purposes (Research sample will be saved in a "Red Top Vacutainer® Tube).

Statistical design and data handling: At the end of the study, we will have lactulose:mannitol ratios (a single value) from each subject at each time-point: Visit #2, and Visit #3. Change in ratio between visits will be plotted for each subject separately so that trends in a given subject can be detected. Following this, ratios from all 12 subjects in each cohort separately) will be averaged from each visit. Means and standard deviations will be determined and values from each visit will be compared using ANOVA followed by paired sample comparison. Finally, we will compare the three cohorts to one another in order to determine if differences between healthy subjects, those with UC, and those with IBS-D can be detected prior to intervention and to determine if intervention influences values in one cohort more than the other.

Relationship to main study: Other events. In other respects, subject interactions will be similar to those in the parent study. See Sections 8 (Adverse Events), 9 (Stopping Rules) and 10 (Data Management) from the parent study.

COVID-19 contingency plan: If final visits are delayed due to COVID-19 circumstances, the research pharmacy may dispense an additional 30-day supply of capsules, up to three times, and the study team may collect additional safety measurements (for example, assessments of AEs via phone).

CITATIONS

1. Coskun M. Intestinal epithelium in inflammatory bowel disease. *Front Med (Lausanne)*. 2014;1:24. doi: 10.3389/fmed.2014.00024. PubMed PMID: 25593900; PubMed Central PMCID: PMC4292184.
2. Salim SaY, Söderholm JD. Importance of disrupted intestinal barrier in inflammatory bowel diseases. *Inflammatory bowel diseases*. 2011;17(1):362-81.

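### Neither UC entry route requires an unchanged maintenance regimen before baseline, and the mild-UC route has no clear minimum duration, so in a single-arm pre/post cohort a response to a recent regimen change can be read as an Aquamin effect

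*Combined protocol and SAP*

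**What the plan says.** Under *Inclusion Criteria for subjects with ulcerative colitis*, a subject qualifies after at least three months of stable remission, untreated or "with a maintenance therapy (except steroids and antibiotics for 3 months) OR have mild ulcerative colitis". The first exclusion on disease activity reads: "Participants must not be felt to have active ulcerative colitis for 3 months before study enrollment (with the exception of mild ulcerative colitis"). Neither list mentions the dose or regimen of UC maintenance therapy. The same inclusion item allows corticosteroids and antibiotics for a flare after enrolment.

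The Introduction describes the 12 UC subjects as being in remission. *Approach* says only "We will recruit and enroll 12 subjects with UC" and takes the criteria from the parent study, whose title covers both mild UC and UC in remission.

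On design, *Approach* states: "Please note that in the proposed study, there will be no placebo group". The primary outcome is barrier function, "evaluated by a change in the lactulose:mannitol ratio in urine by comparing values at 90-days (post-intervention) to baseline (pre-intervention) levels". Under *Statistical design and data handling*, "values from each visit will be compared using ANOVA followed by paired sample comparison", and the cohorts are then compared, among other things "to determine if intervention influences values in one cohort more than the other". No adjustment for therapy or disease activity is described. The Schedule of Events records concomitant medication at screening, baseline, the monthly contacts and the final visit, but no analysis rule uses that record.

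**The concern.** In a cohort without a concurrent control, everything that changes between Day 0 and Day 90 enters the estimate. Eligibility is then the main protection against background drift. The Introduction itself links UC to barrier defects, so a subject still responding to a changed UC regimen could plausibly show a changed lactulose:mannitol ratio whatever Aquamin does.

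Two results are exposed. One is the within-cohort UC change. The other is the question of whether the intervention acts more strongly in one cohort than another, since healthy subjects have no UC regimen that could have been altered just before baseline.

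**Working it through.** **1. Reading the criteria against three hypothetical subjects** (all other criteria met)

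| Subject | Exclusion read as tolerating only mild activity in the window | Exclusion read as exempting the whole mild route |
|---|---|---|
| A. In stable remission for 3 months; maintenance dose changed two weeks before Visit 2 | Eligible | Eligible |
| B. Mild UC throughout 3 months; UC drug changed two weeks before Visit 2 | Eligible | Eligible |
| C. Moderate or severe flare within 3 months; now mild | Excluded | Eligible |

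Subjects A and B show the gap on either reading. Subject C turns on an ambiguity. If the Introduction's description governs, B and C fall outside the cohort and only A remains.

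A related mismatch bears on the mild route. The three-month steroid and antibiotic clause stands before the OR, inside the remission route. The Visit 1 text says that steroids are already on the exclusion list, but the UC list does not contain them. The Visit 1 washout for steroids and antibiotics has no stated length. These texts need reconciling.

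**2. Size: nothing to reproduce**

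The plan gives 12 subjects per cohort (3 × 12 = 36) with no effect size, SD, alpha or power. It gives no share of subjects with recent regimen changes and no amount of drift. The rest of this section is therefore illustration on assumed inputs.

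**3. Shift in the cohort mean**

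With equal baselines and arithmetic means, the spurious relative fall = (number affected / 12) × individual fall:

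- 2 of 12 falling 30%: (2/12) × 30% = 5%
- 3 of 12 falling 40%: (3/12) × 40% = 10%
- 4 of 12 falling 50%: (4/12) × 50% = 16.7%

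**4. Effect on the test**

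Let *k* of 12 subjects drift downward by *s* SDs of the within-subject change, with no Aquamin effect. The bias in the mean change is *k* × *s* / 12 SD; for *k* = 6 and *s* = 1.0 it is 6 × 1.0 / 12 = 0.50 SD. For scale, a two-sided paired t-test at 0.05 with n = 12 has 80% power for a true change of about 0.89 SD.

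Simulated chance of a significant apparent improvement (normal changes, 100,000 runs per setting; nominal 2.5% in that direction):

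| *k* of 12 | *s* = 0.5 | *s* = 1.0 | *s* = 1.5 |
|---|---|---|---|
| 3 | 5% | 9% | 12% |
| 6 | 11% | 27% | 45% |
| 9 | 21% | 59% | 87% |

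Comparing the UC change with the healthy cohort's change does not remove the bias. With *k* = 6, the two-sided rejection rate is 9%, 18% and 32% for the same values of *s*, against a nominal 5%.

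**5. Direction**

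These figures assume that every affected subject improves. If *a* subjects fall and *b* rise by *s*, the bias is (*a* − *b*) × *s* / 12. With 3 falling and 3 rising it is (3 − 3) × *s* / 12 = 0, and the drift adds noise instead. A net rise would mask a benefit.

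**The case against.** Several points against the concern have force.

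- **The remission route is already guarded.** It demands three months of stable remission and the same interval without steroids or antibiotics. A reader might infer that subjects still recovering from a flare enter by this route; the text does not support that. What it lacks is a statement about the maintenance regimen.
- **The mild route is not wholly unguarded.** A reader might infer that it has no stability requirement at all. On a natural reading, the activity exclusion bars anyone who was worse than mild in the preceding three months. The wording is ambiguous, however, and on either reading subject B enters.
- **The IBS-D criteria are not a clean contrast.** They say "the patients are allowed to be on the following medications throughout the study as long as the dosage and regimen is stable", from which a reader might infer that IBS-D background therapy must be stable while UC therapy need not be. That clause covers listed mood medications only and sets no look-back before baseline, so it is no precedent for one. Daily drugs for GI symptoms are dealt with there by exclusion.
- **Some drift would be visible.** CRP and the IBDQ are collected in UC subjects at Visits 2 and 3, and each subject's change is plotted. This helps interpretation, but no rule uses these data, and they would not show whether a shift came from Aquamin or from a changed UC regimen.
- **The root cause is the openly stated single-arm design.** This stands. An eligibility condition removes one source of bias; it does not make the change attributable to Aquamin.

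**Conclusion.** The point holds in a limited form. The criteria do not require an unchanged UC maintenance regimen before baseline on either route. The mild-UC route has no minimum duration beyond an ambiguous exclusion, and the documents disagree on whether mild UC belongs in the cohort. With no control group, a response to a recent regimen change would be counted in the UC result and in the between-cohort comparison.

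The size cannot be stated. The 5% to 17% shifts and the inflated error rates rest on assumed shares, amounts and a common downward direction. With 3 of 12 affected, the false-improvement rate rises only to between 5% and 12%; the large figures need half the cohort or more. A reader might infer that the UC result is likely to be falsely positive. The documents do not support that: they do not say how many subjects will have had a recent change, and their own provision for flares after enrolment shows that drift may also go upward. This is a worthwhile, inexpensive improvement and not a defect that invalidates the study.

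**What to change.** 1. **Reconcile the texts.** State whether mild UC is eligible, since the Introduction and the UC inclusion criteria differ, and what the three-month activity exclusion means for mild UC. The choice is the sponsor's.
2. **Add one eligibility condition.** The UC maintenance regimen, or the absence of one, was unchanged over the protocol's existing three-month look-back before Visit 2. This governs entry only; it neither directs nor withholds treatment.
3. **Use the medication record already collected.** Flag UC-regimen changes in the look-back window (for subjects already enrolled) and after Day 0. Keep the full-cohort UC result as primary. Beside it, report the UC change without subjects with a pre-baseline change, and separately by remission or mild status.
4. **Label post-baseline exclusions with care.** Any result that drops subjects whose regimen changed after Day 0 should be presented as a sensitivity analysis that may favour Aquamin, because it can remove those who flared.

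The cost is one eligibility sentence, a clarification and a short reporting rule, with no new visit or assay. The protocol does not say how far back the Visit 1 medication questions reach, so the look-back flag may need a check of earlier records. Some candidates will wait or be screened out, so filling the 12 UC places may take longer.

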When subjects arrive at the MCRU, they will bring their urine samples with them. Vital signs will be assessed (as in Visit #1). Morphometric measurements (height, weight, and waist/hip measurements) will be collected. Urine Pregnancy test will be performed (if applicable). Subjects will again have the study purpose and methods explained. At that point, they may resume normal food and water consumption. The blood will be drawn and analyzed per metabolic panel test. In addition, a blood sample will be collected and saved for future research purposes, e.g., to conduct barrier permeability assay. The quantity of blood collected will be equivalent to about three teaspoons or 14 ml at each blood collection event. For subjects with UC, C-Reactive Protein (CRP) in blood will be assessed. Subjects with UC will also answer a disease-related questionnaire known as Inflammatory Bowel Disease Questionnaire (IBDQ). Subjects with IBS-D will answer a disease related questionnaire known as, the IBS quality of life questionnaire (IBS-QOL).

After the completion of the 24-hour urine collection, subjects will be given a 90-day supply of Aquamin® along with instructions for taking the agent. Dietary History questionnaire will be administered past year food intake. After 90 days on the intervention, subjects will return to the MCRU for Study Visit #3 (final visit). Visit #3 will be conducted in a manner similar to that of Visit #2. A payment of \$20.00 for completion of Visit #2 will be arranged.

Monthly monitoring: Day 30 and 60 (± 5 days), assessed toxicity, adherence and reminded about diet health questionnaire by telephone or email.

Study Visit #3 (day-90) (Endpoint Visit): On Day 90 (± 5 days), subjects will be asked the same questions as at Visit #2. In addition, they will be asked questions about their experience with the study agents and, in particular, if there were any tolerability issues or safety concerns.

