When subjects arrive at the MCRU, they will bring their urine samples with them. Vital signs will be assessed (as in Visit #1). Morphometric measurements (weight and waist/hip measurements) will be collected. Subjects will again have the study purpose and methods explained. At that point, they may resume normal food and water consumption. The blood will be drawn and analyzed per metabolic panel test. In addition, a blood sample will be collected and saved for future research purposes, e.g., to conduct barrier permeability assay. For subjects with UC, C-Reactive Protein (CRP) in blood will be assessed. Subjects with UC will also answer a disease related questionnaire known as Inflammatory Bowel Disease Questionnaire (IBDQ). Subjects with IBS-D will answer a disease-related questionnaire known as, the IBS quality of life questionnaire (IBS-QOL).

The completion of Visit #3 will conclude the study participation and subject will return all the unused capsules with the capsule log, and disease-related survey (UC or IBS-D) and Dietary History Questionnaire collected. A payment of \$40.00 for completion of Visit 3 will be arranged.

Lactulose:mannitol ratio to assess gastrointestinal permeability. When all of the samples from a given subject have been collected, the samples will be assayed in one batch. The *BioAssay Systems EnzyChrom Assay Kit* will be used for this.

Schedule of Events.

Evaluation/Procedures	Screening- visit 1	Baseline- visit 2 Day 0	^A Monthly Monitoring	Final- visit 3 Day 90±5
Informed Consent	X			
Medical History	X			X
Morphometric measurements ^B		X		X
Urine Pregnancy Test ^C	X	X		
Concomitant Medication/ Supplement Use/ normal diet	X	X	X	X
Disease assessment by IBDQ (UC subjects only) ^D		X		X
Disease assessment by IBS-QOL (IBS-D subjects only) ^D		X		X
Drug assignment (Single group)		X		
Dispense Lactulose/Mannitol	X	X		
Dispense Study Medication		X		
Adherence/Toxicity Evaluation/ Adverse Events		X	X	X
Dietary History Questionnaire ^E		X	X	X
Off-Study Form				X
Pill Count				X
Blood draw ^F		X		X
Urine collection (for Lactulose:Mannitol ratio) / Fluid intake form		X		X

^A Monitoring (for assessment of toxicity, adherence and a reminder to complete the diet questionnaire) will be completed by phone call or email reminder on the following days; Days 30, and 60 (+/- 5 days).

^B Morphometric measurements will consist of body weight, height, and waist/hip measurements. Height will be measured only on Visit 2.

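### A single 90-day capsule supply does not cover a final-visit window that runs to Day 95, so a fully adherent late attender can reach the primary test after 3 to 4 undosed days

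*Combined protocol and SAP*

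**What the plan says.** The Study aim describes Aquamin "taken daily, standardized to 800 mg of calcium per day for 90 days". The primary outcome is the change in urinary lactulose:mannitol ratio, "comparing values at 90-days (post-intervention) to baseline (pre-intervention) levels".

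On supply, the Visit #2 text states: "After the completion of the 24-hour urine collection, subjects will be given a 90-day supply of Aquamin". The Schedule of Events shows study medication dispensed at Visit 2 only.

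On timing, the Study Visit #3 text states: "On Day 90 (± 5 days), subjects will be asked the same questions as at Visit #2". The Schedule of Events gives the same ±5 days for the column that contains the final urine collection. The Visit #2 text adds: "Visit #3 will be conducted in a manner similar to that of Visit #2".

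The COVID-19 contingency plan contains the only resupply provision: "If final visits are delayed due to COVID-19 circumstances, the research pharmacy may dispense an additional 30-day supply of capsules, up to three times".

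At the end, "subject will return all the unused capsules with the capsule log", and a pill count is scheduled. Under Statistical design and data handling, "we will have lactulose:mannitol ratios (a single value) from each subject at each time-point: Visit #2, and Visit #3", and these values are averaged within each cohort of 12.

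**The concern.** The supply and the visit window were set separately and do not match at the late end. A subject seen early in the window is still taking capsules when the sugar test is done. A fully adherent subject seen at the end of the window has run out some days before. Both contribute one Visit 3 ratio to the same cohort mean.

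There is no placebo group, so the change from baseline is the whole treatment estimate. If any effect on permeability fades after the last capsule, late attenders would show less of it and the cohort's on-treatment change would be diluted. The plan controls fasting, diet, fluid and aspirin around the test in some detail, but the supplied text does not say whether the study agent should continue up to it.

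**Working it through.** The plan states no figure for this interval, so there is nothing to reproduce. The check is calendar arithmetic.

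**Inputs from the document.** 90 daily doses (Study aim; Visit #2). Visit day V from 85 to 95, which is 11 permitted days (Study Visit #3; Schedule of Events).

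**Inputs the document leaves open.** The day of the first capsule, and whether the drink falls on the visit day or the day before. The subject brings a completed 24-hour collection, which points to the day before; the fasting instruction refers to the morning of the visit, which could mean the same day. Three combinations are feasible:

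- A: first capsule Day 0, drink on day V − 1
- B: first capsule Day 1, drink on day V − 1
- C: first capsule Day 1, drink on day V

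A first capsule on Day 0 with a same-day drink is excluded. Visit 3 is run like Visit 2, so the baseline collection would then end on Day 1, and capsules are given only after it.

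**Formulas.** Last capsule day = first capsule day + 90 − 1, which is Day 89 under A and Day 90 under B and C. Gap = drink day − last capsule day. Full undosed days = max(gap − 1, 0).

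| Visit 3 day | A: gap / undosed | B: gap / undosed | C: gap / undosed |
|---|---|---|---|
| 91 | 1 / 0 | 0 / 0 | 1 / 0 |
| 92 | 2 / 1 | 1 / 0 | 2 / 1 |
| 93 | 3 / 2 | 2 / 1 | 3 / 2 |
| 94 | 4 / 3 | 3 / 2 | 4 / 3 |
| 95 | 5 / 4 | 4 / 3 | 5 / 4 |

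So 4, 3 and 4 of the 11 permitted days carry at least one full undosed day under A, B and C. No visit up to Day 91 does, under any of the three.

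**Early end.** At V = 85 a fully adherent subject has taken 84, 83 or 84 doses before the drink day, has 6, 7 or 6 left, and was dosed the day before.

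**Supply needed.** To dose through the day before a Day 95 drink takes Days 0 to 93 = 94 doses (A), Days 1 to 93 = 93 (B) or Days 1 to 94 = 94 (C). The shortfall against 90 is 4, 3 or 4.

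**Can the pill count reveal it?** Not alone. At Day 95, an empty bottle fits a subject who took all 90 doses on schedule and then ran out. It also fits one who skipped 3 to 4 doses and was still dosing the day before the drink. Dated log entries would separate the two, but the log's fields are not shown.

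**The case against.** The strongest reply is that the plan intends a fixed course followed by a test. The aim specifies 90 days, the outcome is labelled post-intervention, and the Visit #2 text has subjects return after 90 days on the agent. A 90-day supply delivers exactly that, and ±5 days is ordinary scheduling tolerance. This reading is possible, but it does not fit well. The window opens at Day 85, before a 90-day course can be complete, and the COVID-19 provision suggests that subjects waiting for a delayed final visit were expected to keep dosing.

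Second, overage or a dosing rule may sit in parent-study Section 5 or in the instructions handed out with the capsules, neither of which was supplied. That stands as a caveat, so a reader should not infer that no such rule exists anywhere. It does not undo the explicit 90-day quantity in this protocol.

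Third, few subjects may be affected: only those seen in the last 3 to 4 days of the window and with near-perfect adherence. That also stands.

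A reader might go further and infer a definite loss of effect or power, or a bias between cohorts because one attends later than another. The documents support neither. They give no offset time, no distribution of visit dates and no power target, and nothing suggests that attendance differs by cohort. Any figure for lost power would rest wholly on assumed inputs.

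**Conclusion.** The concern holds as a mismatch between two stated rules. With full adherence and no overage, the last capsule falls on Day 89 or 90 while the primary test visit may be as late as Day 95. Days 93 to 95 on every feasible reading, and Day 92 on two of the three, leave at least one full undosed day before the drink. The maximum is 3 to 4 undosed days, or 4 to 5 days from last capsule to drink.

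The consequence for the result cannot be sized from the documents. It is zero if everyone attends by Day 91, or if any effect persists for four days without capsules. Otherwise it would dilute the on-treatment change for late attenders. This is a cheap improvement to the plan, not a demonstrated defect in the primary endpoint. Nor do the documents give a reason to hold the dose on the test day, so none is proposed.

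**What to change.** In the Visit #2 text, dispense 95 days of capsules, and instruct subjects to keep taking the daily dose through the day before the Visit 3 sugar drink. Enter the date of the last capsule on the existing capsule log. Ninety-five covers the maximum need of 94.

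Cost: 5 extra days × 36 subjects = 180 subject-days on 36 × 90 = 3,240, or 5.6% more capsules, plus one instruction, one log entry and the amendment. Late attenders (from Day 92 or 93) would take up to 3 to 4 doses beyond the 90 in the aim. Doses before the drink day would range from 83–84 to 93–94, against 83–84 to 90 now.

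If 90 doses must remain the cap, keep the present supply and close the Visit 3 window at Day 91. That leaves no undosed day before the drink on any feasible reading, and gives up four scheduling days (Days 92 to 95).

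If parent-study Section 5 or the capsule instructions already provide overage, cite that in the Visit #2 text instead.
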